13.3 Determination of sample size

The sample size for this study was selected to be consistent with the research hypothesis as described in Section 2.2.

This study is exploratory and as such the sample size in this study has not been based on obtaining power to detect specific effects. There is not adequate data to do such a powering. However, assuming that the variability is such (SD=1 on logged data) that we would not miss

(80% power) a 50% decrease in neutrophil numbers in the sputum, a sample size of 40 patients (20 per group) would be sufficient.

Details relating to the optional pharmacogenetics component can be found in Appendix D.

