- To investigate the effect of AZD9668 on urine desmosine (marker of tissue degradation)

The Exploratory Objectives are:

- To investigate the effect of AZD9668 on other markers of tissue degradation
- To investigate the effect of AZD9668 on markers of mucus hyper-secretion
- To collect samples for possible retrospective pharmacogenetics analysis to investigate the influence of genotype on pharmacokinetics (and pharmacodynamic response where appropriate). This will not form part of the Clinical Study Report (CSR).

Study design

This is a randomised, double-blind placebo-controlled, parallel group study in patients with bronchiectasis. Forty patients will be randomised to treatment at a ratio of 1:1 (AZD9668:placebo). Patients who complete the study, will be required to attend 10 visits, some of which may be undertaken in their own home.

There will be an optional pharmacogenetics element to collect samples that may be used for the possible retrospective analysis to investigate the influence of genotype on pharmacokinetics (and pharmacodynamic response, where appropriate). Further details can be found in Appendix D.

Target patient population

Male and female (non child bearing potential) patients between 18 and 80 years, with a clinical diagnosis of idiopathic or post-infective bronchiectasis as confirmed by historical high resolution computerised tomography (HRCT) or bronchogram.

Investigational product, dosage and mode of administration

AZD9668 will be administered orally as a dose of 60 mg (2 x 30mg tablets) twice a day (b.i.d) for 28 days.

Comparator, dosage and mode of administration

Matching placebo tablets will be administered orally, two tablets, twice a day (b.i.d) for 28 days

Duration of treatment

Treatment will continue for 28 days unless any of the discontinuation criteria are met.

Outcome variable(s):

Primary variables

- Sputum neutrophils:
 - Absolute and percentage neutrophil cell count
- Signs and symptoms of bronchiectasis:
 - Bronkotest[®] diary card data
 - Weight of 24 hour sputum collection (pre-treatment versus end of treatment)
 - Quality of life as assessed by St George's Respiratory Questionnaire
 - Lung function tests: (Forced expiratory volume in one second [FEV₁], Slow vital capacity [SVC], Forced vital capacity [FVC], forced expiratory flow between 25 and 75% of forced vital capacity [FEF₂₅₋₇₅])

Secondary variables

- Safety variables

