13.2 Methods of statistical analyses

The outcome variables from the Bronkotest[®] diary card, lung function, sputum and blood collections will be compared between AZD9668 and placebo using an analysis of variance model with fixed factors treatment and country (or centre) and using baseline as a covariate. As the study is exploratory in nature, a p-value of <0.1 will be considered significant. A 2-sided 90% confidence interval will be constructed for the treatment difference and p-values given. For variables with a skewed distribution, data may be log-transformed prior to analysis or a non-parametric test (Wilcoxon rank sum) used instead.

The sputum samples: waking sample, the 2 hour collection and the 1 to 2 hour post dose samples will be analysed separately, with the 2 hour sample being the primary sample for data analysis.

All data will be listed, and will be summarised and plotted as appropriate, further details of the output to be produced will be contained in the SAP.

Withdrawal rates will be compared graphically between AZD9668 and placebo and may be investigated further.

Adverse events will be analysed by means of descriptive statistics and qualitative analysis. AEs will be listed for each patient and summarised by System Organ Class and preferred term assigned to event by using MedDRA.

Concomitant medications will be classified according to the WHO Drug Dictionary, the ATC system and the CPMP route of administration dictionary. All concomitant medications reported at entry and recorded during the study will be listed.

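### The 80% power quoted in Protocol Section 13.3 does not match the two-sided 10% test in Section 13.2, which gives about 69% on the stated assumptions

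*Protocol*

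**What the plan says.** Protocol Section 13.3 first says that the study is exploratory, that its size was not chosen to give power for particular effects, and that there are too few data to do so. It then makes one conditional statement, "assuming that the variability is such (SD=1 on logged data) that we would not miss", and completes it with "80% power) a 50% decrease in neutrophil numbers in the sputum, a sample size of 40 patients (20 per group) would be sufficient". No significance level, sidedness or log base is given there. Nor does it say whether the SD is before or after adjustment for baseline.

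The decision criterion is in Section 13.2 and is repeated in the synopsis: "a p-value of <0.1 will be considered significant. A 2-sided 90% confidence interval will be constructed for the treatment difference and p-values given". The model is an "analysis of variance model with fixed factors treatment and country (or centre) and using baseline as a covariate". For skewed variables, "data may be log-transformed prior to analysis or a non-parametric test (Wilcoxon rank sum) used instead". The synopsis fixes equal allocation: "Forty patients will be randomised to treatment at a ratio of 1:1 (AZD9668:placebo". No one-sided test appears anywhere in the protocol.

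**The concern.** A two-sided 90% interval read alongside p<0.1 is a two-sided test at 10%, with 5% in each tail. A power statement is tied to the test that will be used. With the inputs in Section 13.3, the 80% does not come out under that test. It does come out, at exactly 20 per group, if the whole 10% is put in one tail.

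This is the only quantitative support in the protocol for 40 patients, and it concerns a primary variable in a proof-of-principle study. It is also worded as assurance that a halving of neutrophils would not be missed. If the miss rate on those assumptions is nearer 31% than 20%, a reader of a non-significant neutrophil result would give it somewhat more weight than the design supports.

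**Working it through.** **Inputs**
- Effect: a 50% decrease (Section 13.3). On the natural-log scale, δ = ln 2 = 0.693.
- SD: σ = 1 on logged data (Section 13.3). Natural logs, and σ as the SD of the analysed outcome, are assumptions; the protocol states neither.
- n = 20 per group, 1:1 (Section 13.3, synopsis).
- Criterion: two-sided, α = 0.10 (Section 13.2).

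**Formula.** Noncentrality = δ / (σ√(2/n)) = 0.693 / √(2/20) = 0.693 / 0.316 = 2.19, with 2×20 − 2 = 38 degrees of freedom. Power is the probability that a noncentral t with these values exceeds the critical value. The normal approximation is Φ(2.19 − z).

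**Reproducing the stated figure**

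| Test | Critical t | Power, exact t | Power, normal |
|---|---|---|---|
| One-sided 10% | 1.304 | 81.2% | 81.9% |
| Two-sided 10% (Section 13.2) | 1.686 | 69.4% | 70.8% |
| Two-sided 5% | 2.024 | 57.0% | 59.2% |

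Under the one-sided 10% test, 19 per group gives 79.7% and 20 gives 81.2%, so 20 is the smallest group size reaching 80%. That match suggests, but does not prove, that 0.10 was entered in one tail.

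**What 80% requires at two-sided 10%** (one input changed at a time)
- Group size: the normal formula gives 2(1.645 + 0.842)²/0.693² = 25.7, so 26. By exact t, 26 gives 79.4% and 27 gives 80.7%.
- Effect, at 20 per group: δ = 0.801, a decrease of 1 − e^(−0.801) = 55.1%.
- SD, at 20 per group: about 0.87 by exact t (0.88 by normal approximation).

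**Baseline adjustment.** If σ = 1 is the SD before adjustment and ρ is the baseline–outcome correlation, the residual SD is √(1 − ρ²). With ρ = 0.5 this is √0.75 = 0.866, the noncentrality is 0.693/(0.866 × 0.316) = 2.53, and power on 36 degrees of freedom is 79.9% (81.2% normal). With ρ = 0.3 it is 72.9% by exact t, and with ρ = 0.6 it is 85.2%.

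**Log base.** If SD=1 were on log2, δ = 1 and two-sided 10% power is 92.8%. On log10, δ = 0.301 and it is 24%. Neither gives 80%.

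**The case against.** The strongest answer is the baseline covariate. Section 13.2 adjusts for baseline, and Section 12.2.1 takes both baseline and end-of-treatment counts as means over up to three visits, so a correlation of 0.5 is not far-fetched. If SD=1 is the unadjusted SD, two-sided 10% power is then close to 80%. For that reason a reader who infers that the 80% can come only from a one-sided test goes too far. What stands against the answer is that Section 13.3 gives no correlation, does not mention adjustment, and does not say which SD it means. The 80% therefore cannot be obtained from what is written.

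The second answer is the disclaimer. Section 13.3 says that the size was not based on power and that data are inadequate for powering. A residual SD of 0.87 instead of 1 is well within that uncertainty, and the 90% confidence interval will show the precision actually achieved. This lowers the consequence and stands. It does not make the conditional statement correct, because that statement takes SD=1 as given.

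Third, Section 13.3 claims sufficiency rather than exactly 80%, and log2 would exceed it. But natural log is the only one of the three bases that reproduces 20 per group at 80% under a test tried here.

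A reader might also infer that Section 13.2 is deficient because it leaves the log transformation and the choice of country or centre open. Those choices can properly be settled in the SAP, which Section 13 says will be prepared before database lock and unblinding. The rank-test option hardly matters to this point: with a relative efficiency of 0.955, two-sided 10% power is 69.0%, against 70.8% on the same normal approximation.

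**Conclusion.** The concern holds as a mismatch between two statements in the protocol. With natural logs and SD=1 as the SD of the analysed outcome, the Section 13.2 criterion gives about 69% power (71% by normal approximation), some 10 points below the 80% in Section 13.3. It rests on those two assumptions. The log base is the likelier reading because it reproduces the planned group size; the meaning of the SD is open. The figure is for a plain two-group comparison. Two fewer degrees of freedom, at the same residual SD, leave it at 69.3%.

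Severity is moderate. A reader might infer that the trial is too small and should recruit 27 per group. The documents do not support that, because the sample size is explicitly not justified by power. What is wrong is the quoted figure and its missing conditions.

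**What to change.** Restate the sentence in Section 13.3 along these lines: *with a two-sided 10% test and a residual SD of 1 on the natural-log scale, 20 per group gives about 70% power for a 50% decrease in sputum neutrophil count, or 80% power for about a 55% decrease.* This names alpha, sidedness, log base and which SD is meant.

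If the sponsor prefers to keep 80% for a 50% decrease, Section 13.3 should state what it relies on: a baseline correlation of about 0.5 with an unadjusted SD of 1, or equivalently a residual SD of about 0.87, with the basis for that value.

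The cost is one sentence and, in the first form, a less favourable power figure. Sample size, significance level, exploratory status and Section 13.2 stay as they are.

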13.4 Interim analyses

No interim analysis is planned.

13.5 Data monitoring committee (Not Applicable)

Not applicable to this study. There will be no data monitoring committees involved.

